1.10 Clinical Study Plan

The primary goal of this human pilot study is to translate the novel imaging agent LS301, which selectively identifies breast cancer cells with high accuracy, to human patients. Diverse animal models of breast cancer have been investigated to surgical removal of spontaneous, disseminated, and diffuse tumors, which were detected to single cancer cell level by LS301. We have also shown that the NIR fluorescence can be captured efficiently using CVG.

The maximum recommended starting dose (MRSD) for this clinical trial was based on the NOAEL from animal studies. As shown in the GLP toxicology document, the NOAEL from the rat toxicity study is 10 mg/kg for females and 0.5 mg/kg for male rats, which is equivalent to human equivalent dose (HED) of 1.6 mg/kg and 0.081 mg/kg, respectively. Applying a safety margin (typically 10-fold) to the NOAEL gives MRSD of 0.16 mg/kg based on female NOAEL and 0.0081 mg/kg based on the NOAEL in male rats. The highest non-severely toxic dose (HNSTD) in the rat toxicity study was determined to be 10 mg/kg (HED 1.6 mg/kg) in both male and female rats. Another approach that is considered appropriate to determine a safe starting dose is using 1/6th of the HNSTD in a more sensitive species. Based on the NOAEL and HNSTD from the rat toxicity study, the maximum recommended safe dose to test in the FIH study was estimated to be between 0.16 and 0.26 mg/kg. While previous investigations with LS301 in mice showed the lowest detectable dose with the CVG to be 0.075 mg/kg (equivalent to HED of 0.006 mg/kg), an anticipated optimal starting dose of 0.1 mg/kg will be used as the starting dose in the clinical study. This dose is well within the estimated range for the MRSD estimated from the rat toxicity study.

We propose a phase 1 rolling six dose-escalating design given that this is the first-in-human use of LS301, followed by a phase 2 trial for preliminary evaluation of its diagnostic capabilities (including sensitivity and specificity). During phase 1, LS301 will be administered intravenously to a cohort of six patients at a dose of 0.05 mg/kg; if fewer than 2 DLTs are observed, LS301 will be given at the next high dose level of 0.075 mg/kg; if fewer than 2 DLTs are observed, LS301 will be given at the expected optimal dose of 0.1 mg/kg. Once safety is confirmed and the optimal imaging dose is established, an additional 9 patients will be enrolled in the phase 1 expansion cohort to evaluate for safety.

After phase 1 data has been submitted to and discussed with the FDA, an additional cohort of 88 patients will be enrolled to the phase 2 portion of the trial to assess the diagnostic capabilities of LS301 for identification of positive margins at surgery. Based on preclinical studies^{36,37,40,43,68}, the anticipated optimal dose for LS301 is 0.1 mg/kg body weight (BW). This dose is a fraction of ICG concentration currently approved for human use. LS301 will be formulated in 1% human serum albumin (HSA) in saline and administered intravenously as a slow infusion over 5-10 minutes. Based on LS301 in 1% HSA and assuming a 60 kg adult with 1.6 m² surface area and using the conversion factor $k_m = 60/1.6 = 37 \text{ kg/m}^2$, the equivalent dose is $100 \mu\text{g/kg} \times 37 \text{ kg/m}^2 = 3.7 \text{ mg/m}^2$.

In all patients, LS301 will be administered 4-24 hours before lumpectomy. LS301 uptake in primary breast cancer or SLN versus uninvolved tissue will be visualized with the CVG system during surgery by a member (operating or non-operating) of the surgical team. The NIR light source for the CVG is based on light-emitting diodes (LEDs) or laser light operating at 15-20 mW/cm² output at tissue, which can deliver sufficient light to biological tissues and induce fluorescence emission to meet the needs of the planned clinical studies. It should be noted that the light source is below the US FDA recommended limit for NIR exposure and ANSI standard. The fluorescence signals will be received by the detector portion of our device. Gain-settings could be easily adjusted during operation to optimize the contrast between high fluorescence areas (tumors) and low fluorescence areas (normal tissues). Real-time fluorescence image will be displayed in the goggle eyepiece as well as on a secondary monitor to facilitate viewing by other members of the surgical team in the OR. Images from the CVG or SPY will not be used to alter the surgical plan in any way.

Fluorescence in the excised tissue at the margins will be determined by quantitative near-infrared fluorescence microscopy. For each patient, at least 4 specimens from excised tissue will be analyzed, including suspected tumor and suspected healthy tissue. De-identified data will be stored on a computer. Stored information will only have coded numbers and not the names of the patients to ensure patient privacy.

1.11 Rationale

Our preclinical data have demonstrated the feasibility of fluorescence-guided tumor resection by our CVG with LS301 in animal models. In this study, we will conduct intraoperative imaging procedures that have minimal interference with ongoing surgery. The underlying hypothesis is that the accurate detection of all cancer cells highlighted by LS301 during surgery will reduce the number of breast cancer patients with margin positivity to less than 5%, compared to the current surgical paradigm of greater than 20%. The pilot study will obtain critical data required to address the larger question of surgical margin assessment in a full phase I clinical trial.

1.12 Potential Contribution

The ability to identify tumors *in vivo* would be a highly useful clinical tool for oncologic surgeons. When utilized in tumor resection, including SLN biopsy, the proposed procedures can readily detect tumor margins, small nodules, residual tumors, and positive SLNs, thereby reducing the incidence of incomplete resection, the size of healthy tissues resected, and the need for revision surgeries. Moreover, the proposed technology can also offer high spatial resolution in real-time without the use of radioactive tracers. In addition to improving healthcare, the approach can potentially shorten OR time to further reduce cost of surgery. Therefore, the LS301-mediated fluorescence imaging of tumors has high potential impact on breast cancer management.

2.0 OBJECTIVES

2.1 Primary Objectives

Phase 1: to determine the safety and optimal imaging dose of LS301 injected in breast cancer patients.

Phase 2: to determine the ability of this novel fluorescence imaging agent to predict the presence of positive margins around partial mastectomy specimens and positive SLNs during surgical therapy for breast cancer.

3.0 PATIENT SELECTION

3.1 Inclusion Criteria

1. Newly diagnosed Stage I-II breast cancer patients undergoing breast-conserving therapy and SLN biopsy.
2. Negative nodal basin clinical exam.
3. At least 18 years of age.
4. Able to understand and willing to sign a written informed consent document.

3.2 Exclusion Criteria

1. Contraindications for surgery.
2. Receiving any investigational agents.
3. History of allergic reactions attributed to ICG or other agents used in the study, include known iodide or seafood allergy. We do not expect many of these adverse reactions with LS301 because it is not radioactive and does not possess iodinated counterions.
4. Presence of underlying lung disease.
5. Pregnant. Female patients of childbearing potential must have a negative serum or urine pregnancy test no more than 7 days before start of participation.
6. Breastfeeding. Patients who are breastfeeding are excluded from this study because there is an unknown but potential risk for adverse events in nursing infants secondary to treatment of the mother with LS301.

3.3 Inclusion of Women and Minorities

Breast cancer is rare in men; therefore, it is likely that only women will enroll in this trial, although men are eligible. People of all races and ethnicities may enroll.

4.0 REGISTRATION PROCEDURES

Patients must not start any protocol intervention prior to registration through the Siteman Cancer Center for phase 1A and UT Southwestern Medical Center Velos database for phase 1B and phase 2.

The following steps must be taken before registering patients to this study:

1. Confirmation of patient eligibility
2. Registration of patient in the Siteman Cancer Center OnCore database for phase 1A and UT Southwestern Medical Center Velos database for phase 1B and phase 2.
3. Assignment of unique patient number (UPN)

4.1 Confirmation of Patient Eligibility

Confirm patient eligibility by collecting the information listed below:

1. Registering MD's name
2. Patient's race, sex, and DOB
3. Three letters (or two letters and a dash) for the patient's initials
4. Copy of signed consent form
5. Completed eligibility checklist, signed and dated by a member of the study team
6. Copy of appropriate source documentation confirming patient eligibility

4.2 Patient Registration in the Siteman Cancer Center OnCore Database for phase 1A UT Southwestern Medical Center Velos Database for phase 1B and phase 2.

All patients must be registered through the Siteman Cancer Center OnCore database for phase 1A UT Southwestern Medical Center Velos database for phase 1B and phase 2.

4.3 Assignment of UPN

Each patient will be identified with a unique patient number (UPN) for this study. All data will be recorded with this identification number on the appropriate CRFs.

4.4 Baseline Data Collection

1. Patient demographic information: age, sex, race, ethnicity
2. Patient height, weight, and body mass index (BMI)
3. Patient medical history and concomitant medications

5.0 STUDY PROCEDURES

5.1 LS301 Preparation

LS301 will be prepared under cGMP protocol and supplied in an amber-colored vial as a lyophilized product in 1% HSA/PBS aqueous solution. Each vial will contain 2 mg LS301. Before administration, 10 mL of PBS will be added to the lyophilized powder and mixed by shaking for 1 minute. The aqueous formulation is stable at room temperature for 4 hours or in the refrigerator (2-8°C) for 24 hours. The agent will be administered 4-24 hours before surgery.

5.2 Procedures

5.2.1 Phase 1

A rolling six design (refer to Section 8.1) will be used to enroll patients who are being treated for pathologically proven breast cancer prior to definitive surgical interventions in the phase 1A dose escalating portion of the study, during which LS301 will be administered intravenously at one of three doses (see table below). Patients will be observed for dose-limiting toxicities (DLT) (refer to Section 5.2.1.3).

LS301 Dose Level	LS301 Dose
Level 1 (starting dose)	0.05 mg/kg
Level 2	0.075 mg/kg
Level 3	0.1 mg/kg

The patient will undergo surgery 4-24 hours after administration of LS301 using current best practices. Breast tissue and axillary LNs will be imaged non-invasively prior to start of surgery and excised breast tissue and SLNs will be examined ex vivo for the presence of LS301 fluorescence using our Cancer Vision Goggles (CVG) to determine if LS301 accumulated in the breast cancer. We will quantify fluorescence intensity in the cancer to establish the feasibility of observing LS301 fluorescence with the imaging system.

The dose used in cohort 1 is the lowest dose (0.05mg/kg) and was used exclusively for safety assessment. The investigators did not expect to detect LS301-associated tumor tissue fluorescence before incision at this lowest dose level. Therefore, cohort 1 patients will not be imaged non-invasively to assess tumor tissue fluorescence before incision. Non-invasive tumor fluorescence examination will be initiated from cohort 2 onwards, where higher doses will be used.

Investigators do not expect the 1st dose (0.05 mg/kg) or 2nd dose (0.075 mg/kg) to lead to any detectable fluorescence non-invasively in the axilla before sentinel lymph node excision due to the low concentration of expected LS301 retention in lymph nodes. Therefore, lymph node fluorescence will not be assessed non-invasively before incision for cohorts 1 and 2. Investigators will plan to image lymph node regions non-invasively starting with cohort 3 due to the higher injected dose (0.1 mg/kg).

After the optimal dose has been determined, an additional 9 patients will be enrolled in the phase 1 expansion cohort to evaluate for safety. This expansion cohort is considered phase 1B and will be conducted at UT Southwestern Medical Center.

5.2.1.1 Dose Escalation Schema

LS301 Dose Level	LS301 Dose
Level 1 (starting dose)	0.05 mg/kg
Level 2	0.075 mg/kg
Level 3	0.1 mg/kg

Dose escalation may occur as soon as the last patient in a cohort has completed her one-hour post-injection toxicity monitoring.

5.2.1.2 Definition of Optimal Dose

The optimal dose will be the dose at which fewer than 2 DLTs are observed and optimal image quality is observed. It need not be the maximum tolerated dose if optimal image quality is observed at a lower dose than the MTD.

5.2.1.3 Definition of Dose-Limiting Toxicities

DLT is defined as any grade 2 or above toxicity that occurs during the hour after injection that is considered possibly, probably, or definitely related to LS301.

5.2.1.4 Dose Escalation Criteria

The molecular probe LS301 is an imaging agent binding to breast cancer cells and other malignant cells and will be visualized through by CVG which is a non-significant risk device. Similar to the FDA-approved agent ICG, we do not expect any serious adverse events caused by the agent.

A rolling six design will be used for the phase 1 portion. In the rolling six design, 2 to 6 patients can be enrolled to a dose each time. The dose de-escalation occurs when two or more DLTs occur at a dose level, while dose escalation occurs with 3/3, 4/4, 5/5, 5/6, or 6/6 patients are evaluated without DLT. (Refer to Section 8.1 for further details.)

5.2.2 Phase 2

After data from the phase 1 portion of the study have been submitted to and reviewed by the FDA, and if analysis of the data from phase 1 confirms the safety of administering LS301 in humans and establishes the optimal imaging dose, 88 patients will be enrolled in the phase 2 portion of the study after any necessary protocol revisions have been made based on phase 1 data and FDA approval.

It is expected that the study procedures for phase 2 will be the same as the procedures in phase 1. The optimal imaging dose of LS301 determined in phase 1 will be administered in phase 2.

The breast tissue and axillary LNs will be imaged non-invasively using the CVG and worn by a non-operating member of the surgical team. After removal of the breast cancer and SLNs using current best practice, a member of the surgical team who is not conducting the surgery will wear the CVG to determine if LS301 fluorescence is present at the margin and in SLNs, using a global threshold of 20% signal above background or a dynamic statistical threshold to indicate a positive margin. The accuracy of determining margin positivity will be established by comparing the CVG assessment to histopathology.

5.2.3 Administration of LS301

The patient will undergo intravenous injection of LS301 4-24 hours prior to surgery. A study nurse or other qualified member of the study team will inject the LS301 via IV over 5-10 minutes in the office or pre-op room (as applicable) and will monitor the patient as described in Section 5.4 below. Administration of LS301 will not interfere with the standard of care, including all standard of care for lymph node assessment using ^{99m}Tc Tilmanocept injection on the day of or day before surgery.

5.2.4 Intraoperative Review

The operating surgeon will conduct breast cancer surgery as usual without using a device to visualize LS301 fluorescence. To prevent bias in data acquisition, a non-operating member of the study team will wear the CVG before the start of surgery to examine the breast tissue and axillary LNs non-invasively and at the completion of the surgery to examine the excised tissue, SLNs and surgical cavity. Findings with the study will be recorded but will not change the standard of care. The operating surgeon will remain blinded to the fluorescence images throughout the operation. The examining surgical team member will wear the CVG and image all six anatomical aspects (superior, inferior, anterior, posterior, medial and lateral) of the surgical specimen as well as the surgical cavity for LS301 fluorescence. The SPY system will be used for confirmatory fluorescence imaging and compared with CVG detection of LS301 fluorescence, during phase 2 of the study.

Detection of LS301 fluorescence at the cut edge of the excised specimen will determine margin positivity and presence of fluorescence in the SLNs indicate presence of metastatic cancer cells. Given that CVG can detect LS301 fluorescence in tumors several millimeters deep, investigators will use pathology data to initially train the system by correlating fluorescence intensity to background ratio with pathologist's margin assessment. The information will then be used in phase 2 to predict margin positivity in the OR. The detection of fluorescence on excised tissue without correlative fluorescence in the tumor cavity after lumpectomy will predict

a negative margin for invasive ductal carcinoma. For DCIS, laser power modulation within the approved limit or dual excitation or emission method will be used to estimate the depth of fluorescence source. In general, a signal to background ratio of 1.2 (20% higher intensity than background) will be used as a global threshold to determine margin and SLN positivity status. In addition, a dynamic statistical thresholding approach will be used to delineate the boundary of tissue fluorescence. An intensity-based heat color map will be used for false color representation of the fluorescence to guide the examining surgeon. Areas with high LS301 accumulation, will be represented as red-hot compared to green and blue for surrounding tissue. A continuum of red fluorescence will indicate that the entire excised tissue is cancer. Fluorescence gradient using the heat color map showing red to blue from the edge of tumor tissue will indicate a positive margin. When the fluorescence emanating from tumors away from the margin (> 2 mm), hazy blue fluorescence will be observed at the surgical margin and will be classified as clear margin.

If this simple approach fails to accurately identify positive or clean margins, we will use a dual wavelength excitation for the depth-profiling of fluorescence emission. It is well known that light travels through tissue differently across wavelengths due to wavelength-dependent optical properties. When a fluorophore is excited using two wavelengths, the intensity falloff with depth of each wavelength will be related to the depth of the fluorophore. Because both wavelengths are exciting the same fluorophore concentration, the ratio of the fluorescence generated yields the depth of the fluorophore irrespective of concentration accumulated in the tumor tissue. The depth of fluorescence in the resected sample will be estimated using two spectrally separated NIR wavelengths to excite LS301 fluorescence. The ratio of the emitted intensities imaged for both excitation wavelengths will be closer to one when the tumor tissue is at the cut surface. At higher depths the ratio will deviate away from 1 as the shorter wavelength excitation is attenuated more than longer excitation. A depth map of tissue fluorescence will be created and compared to histopathology for determining the accuracy of predicting positive or clear margin status and SLN metastatic status. The dual-wavelength method will initially be implemented as a standalone portable closed box configuration which will then be miniaturized and implemented in the CVG.

The surgically removed tumor mass and SLNs will be pathologically examined under standard protocols. At least 4 specimens from the excised tissue of a patient, two suspected tumor and two suspected healthy tissue per patient will be analyzed.

The tumor specimens generated after breadloafing by the surgical pathologist will be individually imaged using the CVG and the dual-wavelength closed box imaging system before fixation and paraffin embedding to record the fluorescence intensity localization and depth profiles. Pathologist will provide tissue samples that will be sectioned and mounted on slides. The sectioned tissue slides will be imaged for LS301 fluorescence using high-resolution confocal microscopes. These will be compared to standard Hematoxylin & Eosin staining of tumor tissue to verify

LS301 specificity for cancer cells. Additional immunohistochemistry will be performed on these tissue sections to verify or identify LS301-associated biomarkers.

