1.0 BACKGROUND AND RATIONALE

1.1 Surgical Resection of Breast Cancer and Sentinel Lymph Node Biopsy

Surgical resection is the standard of care for many solid tumors such as breast cancer, and sentinel lymph node (SLN) biopsy is used for cancer staging¹. Before breast surgery, standard imaging methods including mammography and ultrasound are used to identify tumor location. However, these preoperative imaging methods are not able to provide real-time image guidance in the operating room to ensure complete removal of tumors or assess surgical margins. Unfortunately, incomplete tumor removal increases the chances of cancer recurrence by two-fold² and necessitates repeat surgery, whereas inaccurate SLN identification may misdiagnose the cancer stage. Despite recent advances in pre-operative imaging methods, surgeons rely on visual inspection, palpation, and tactile evaluation to distinguish cancer from uninvolved tissue intraoperatively, leading to subjective decision-making and variable outcomes. For example, up to 70%³⁻⁵ of patients undergoing breast-conserving reconstructive surgery (BCS) have positive margins, depending on where the surgery was performed, experience of the surgeon, and the tumor characteristics⁶⁻⁸. For these reasons, we seek to develop an image-guided method for differentiating tumors from surrounding tissues and offer real-time surgical navigation^{10,11}.

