8.0 STATISTICAL CONSIDERATIONS

8.1 Study Design

A rolling six design which is intended for relatively safe trials and shortening the study duration is proposed for the phase 1 portion ⁷⁴. In the rolling six design, three to six patients can be enrolled to a dose each time. The dose de-escalation occurs when two or more DLT occur at a dose level while dose escalation occurs when 3/3, 4/4, 5/5, 5/6 or 6/6 patients are evaluated without DLT ⁷⁵. Three dose levels will be tested in the phase 1 study, 0.05, 0.075 and 0.10 mg/kg. LS301 will be administered intravenously at a starting dose of 0.05 mg/kg to a cohort of six patients and escalate/de-escalate following the decision rule of the rolling six design. Once six patients have been included at the current dose level, inclusions are suspended until at least five of the six patients have completed the procedure without DLT observed in the evaluation period. MTD is hit where two or more patients out of six at a dose level experience DLT. We do not expect any serious adverse events related to LS301 at the initial Dose Level 1. Once the MTD is determined, an expansion cohort with 9 patients will be tested at the MTD and an optimal imaging dose will be recommended for the subsequent phase 2 trial.

At the completion of the expansion cohort, a single arm phase 2 trial will be performed at the optimal imaging dose. A breast surgeon will perform breast conserving surgery per standard of care. At the completion of the surgery, a second investigator (to reduce bias in data collection) will wear the cancer vision goggle (CVG) to visualize the excised tissue to determine if there are any positive margins based on the presence of LS301 fluorescence. If any positive margins are observed, the subject will be considered to have a positive margin; otherwise, the margin is considered negative. The excised tissue will later be examined by a breast cancer pathologist. Standard pathologic techniques will be used to determine if there are positive margins. Particular attention will be paid to the sites marked following CVG assessment to confirm whether the margin is positive or negative at any of these sites, or positive at other locations not identified by CVG. No interventions will be allowed based on the CVG results.

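### The plan masks the surgeon to the CVG images but does not keep operative margin opinion out of the CVG reader's call; that call should be locked before such opinion is shared

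*Combined protocol and SAP*

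**What the plan says.** **Who reads.** Section 5.2.4: "To prevent bias in data acquisition, a non-operating member of the study team will wear the CVG before the start of surgery". Section 5.2.2: "a member of the surgical team who is not conducting the surgery will wear the CVG". Section 8.1 calls this person a second investigator and again gives bias reduction as the reason. Section 1.10 differs: the viewer may be an operating or a non-operating member of the surgical team.

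**When.** Section 5.2.4 places the read "at the completion of the surgery to examine the excised tissue, SLNs and surgical cavity", and 8.1 agrees. Section 5.2.2 says only that it follows removal of the cancer and the SLNs. Histopathology comes later (8.1).

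**How.** Section 5.2.4 sets a signal-to-background ratio of 1.2 as the global threshold. Section 5.2.2 allows that threshold or a dynamic statistical one. Section 5.2.4 adds appearance rules for a heat map, such as: "Fluorescence gradient using the heat color map showing red to blue from the edge of tumor tissue will indicate a positive margin". For invasive ductal carcinoma, the call also uses whether the cavity fluoresces.

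**Masking.** Section 5.2.4 keeps the operating surgeon blinded to the fluorescence images. No section says what the CVG reader may know, or when the call becomes final.

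**The concern.** Using a separate reader protects the surgeon's conduct of the operation from the fluorescence images. It does not protect the fluorescence call from the operation. By the plan's own account, "surgeons rely on visual inspection, palpation, and tactile evaluation to distinguish cancer from uninvolved tissue intraoperatively" (Section 1.1). A surgical-team member who reads after excision may have seen or heard the results of that assessment. Part of the read is a judgement about colour and gradient, and the choice of threshold is open, so a prior suspicion could affect the call.

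Phase 2 asks whether LS301 with the CVG predicts positive margins. If operative opinion enters the call, the trial measures fluorescence combined with ordinary intraoperative judgement and credits the result to the agent. Few positive margins are expected, so one or two altered calls could change the conclusion on sensitivity. Masking that was absent at the time of the read cannot be restored afterwards.

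**Working it through.** **1. Reproduce the plan's figures.** Inputs from Section 8.4: 88 patients, 14 expected positive margins (88 × 0.155 = 13.64), unacceptable sensitivity 0.70, expected sensitivity 0.95, one-sided binomial test, target level 0.05.

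For X detected among 14, P(X ≥ 13) = 14·p^13·(1 − p) + p^14.

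- p = 0.70: 0.0407 + 0.0068 = 0.0475, the attained level in 8.4.
- p = 0.95: 0.3593 + 0.4877 = 0.8470, the stated power of 84.7%.
- Lowering the bar to 12 of 14 gives a level of 0.161, above the target.

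So the test passes only with at least 13 of 14. Section 8.3.2 lists sensitivity as an estimate with a confidence interval; the pass mark comes from 8.4. It would shift if the number of positives is not 14.

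**2. Where a cue would act.** In the table in 8.3.2, a positive margin missed by the CVG is counted in n13 and one correctly located is counted in n22. Sensitivity is n22/(n13 + n22). A cue that rescues a miss moves one tumour from n13 to n22.

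**3. Illustration.** The documents give no rate of cue-driven calls. *Assume* that fluorescence alone has sensitivity 0.70, and that cues turn a share u of the misses into correct calls at the right location. Apparent sensitivity is then 0.70 + 0.30u.

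| Assumed u | Apparent sensitivity | P(X ≥ 13 of 14) |
|---|---|---|
| 0 | 0.700 | 0.0475 |
| 0.10 | 0.730 | 0.0632 + 0.0122 = 0.075 |
| 0.25 | 0.775 | 0.143 |
| 0.50 | 0.850 | 0.357 |

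The last two rows only show how steep the curve is. Nothing in the documents supports shares that large.

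**4. The other direction.** Cues could also add false positives. With 74 expected negatives (88 − 14), specificity passes at 59 or more: the level at 0.70 is 0.041, as stated in 8.4. If specificity fell from 0.95 to an assumed 0.88, P(X ≥ 59 of 74) would still be 0.987. The specificity test would therefore give little warning of cue-driven false positives.

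**5. The masking, side by side.**

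| Information | Kept from the CVG reader? |
|---|---|
| Final histopathology | Yes, in effect: it comes after the call (8.1) |
| Surgeon's margin opinion | Not stated |
| Specimen-imaging or gross margin opinion | Not stated |
| Course of the operation | Not stated |

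**The case against.** The strongest reply has four parts.

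- **The most important masking is in place.** The reader calls and inks the margin before histopathology exists. This stands. A reader of 5.2.4 might infer that the CVG reader is masked to nothing; that goes too far. The text is silent about operative information, which is not the same as specifying an open read.
- **There is a numeric rule, and location must match.** The 1.2 ratio limits discretion, and 8.3.2 counts a true positive only where CVG and histology agree on location. This stands in part. The alternative threshold in 5.2.2 and the heat-map rules in 5.2.4 leave room for judgement, and a surgeon's suspicion can itself point to a location.
- **The direction is not established.** The 14 positives in 8.4 are those expected after standard surgery, so they are margins that the surgeon has already inspected and left. The surgeon's opinion may say little about them, and cues about other walls might mainly add false positives. This stands. A reader might infer that sensitivity will be inflated; the documents do not show that.
- **An earlier specimen read would do harm.** One might want the specimen read as soon as it leaves the field, ahead of the cavity. But the invasive ductal rule in 5.2.4 needs specimen and cavity together, and an earlier read could concern a different margin from the one histopathology reports. Cavity shaves appear in 8.4 only as background to a recall rate. This stands, and the timing should not be moved.

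It may also be tempting to ask for a masked SPY read, since 5.2.4 says: "The SPY system will be used for confirmatory fluorescence imaging and compared with CVG detection of LS301 fluorescence". No analysis in 8.2 or 8.3 uses CVG–SPY agreement, so no stated result depends on it.

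None of this supplies the missing statement of what the reader may know when making the call.

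**Conclusion.** The point holds as a gap in specification. The plan claims a bias control but masks only the surgeon, and it leaves the CVG reader free to use operative margin opinion in a partly visual call. Whether that would raise or lower sensitivity, and by how much, cannot be derived from the documents.

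The size given is conditional. With 14 positives, a true sensitivity of 0.70 and an assumed 10% of misses rescued at the correct location, the chance of passing rises from 4.7% to 7.5%. This shows that a test requiring 13 of 14 is sensitive to small changes in the calls. It is not an estimate of bias in this trial. No change to the sample size follows. The recommendation is a cheap improvement to make before phase 2, when 5.2.2 already provides for protocol revisions.

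**What to change.** 1. In 5.2.4 and 8.1, require the CVG reader to make the per-aspect specimen call, together with the cavity look that the invasive ductal rule needs, from fluorescence and the prespecified threshold only. Since 5.2.2 leaves the choice of threshold open, name the one that governs the call.
2. Enter the call on the Surgery Form with a time stamp, and lock it before the reader is given any surgeon, specimen-imaging or gross-pathology margin opinion.
3. Keep the existing specimen and cavity timing, so that the call refers to the same final margin as histopathology.
4. Reconcile 1.10, which allows an operating member to view, with 5.2.2, 5.2.4 and 8.1.

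The cost is protocol wording, one form field and some discipline about conversation in the operating room. The same reader is used and no patients are added. A reader in the room may still notice things, so the lock reduces the risk without removing it.
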